8.3 Patient screening

It is permissible to re-screen a patient if s/he fails the initial screening or falls outside of the screening window; however, each case must be discussed and agreed with the Sponsor on a case-by-case basis.

Information on what data should be collected for screening failures is outlined in the SOM.

8.4 Patient demographics/other baseline characteristics

Patient demographic and baseline characteristic data will be collected on all patients. Relevant medical history/current medical conditions data will also be collected until signature of informed consent. Details are outlined in the SOM.

Investigators have the discretion to record abnormal test findings on the medical history CRF, if in their judgment, the test abnormality occurred prior to the informed consent signature.

8.5 Efficacy / Pharmacodynamics

Pharmacodynamic measurements will be assessed at the timepoints defined in the [Assessment Schedule](#).

8.5.1 6-minute walk test

Maximum walking distance as assessed by the 6MWT will be used to evaluate functional capacity of PAD patients participating in this study.

In addition to the PD assessment of maximum walking distance, data generated from the 6MWT will also be used to evaluate pain-free walking distance.

Details of the 6MWT will be provided in the SOM, and sites will be provided additional training videos and manuals specific to the conduct and data collection of the 6MWT.

8.6 Safety

Safety assessments are specified below; methods for assessment and recording are specified in the SOM, with the Assessment Schedule ([Section 8.1](#)) detailing when each assessment is to be performed.

8.6.1 Physical examination

See the SOM for details.

8.6.2 Vital signs

- Body temperature
- Blood pressure
- Pulse rate
- Respiratory rate

See the SOM for details.

8.6.3 Height and weight

- Height
- Body weight
- BMI will be calculated as (Body weight (kg) / [Height (m)]²)

See the SOM for details.

8.6.4 Laboratory evaluations

Clinically relevant deviations of laboratory test results occurring during or at completion of the study must be reported and discussed with Novartis personnel. The results should be evaluated for criteria defining an AE and reported as such if the criteria are met. Repeated evaluations are mandatory until normalization of the result(s) or until the change is no longer clinically relevant. In case of doubt, Novartis personnel should be contacted.

Patients should be instructed to fast for at least 8 hours prior to scheduled serum lipid panel collections. Fasting is not required prior to other scheduled lab collections.

Details regarding collection methods and processing are outlined in the Central Laboratory Manual.

Hematology

Hemoglobin, hematocrit, PTT, PT/INR, red blood cell (RBC) count, white blood cell (WBC) count with differentials and platelet count will be measured.

Corporate Confidential Information

Urinalysis

Dipstick measurements for specific gravity, protein, glucose and blood will be performed. Microscopy, WBC, RBC and sediments will also be assessed in case of an abnormal dipstick test.

Coagulation panel

D-dimer, fibrinogen, PTT, PT/INR will be measured as part of the safety labs conducted at the central lab. **Corporate Confidential Information**

8.6.5 Electrocardiogram

Full details of all procedures relating to the ECG collection and reporting are contained in the SOM.

PR interval, QRS duration, and QT intervals will be assessed.

The Fridericia QT correction formula (QTcF) should be used for clinical decisions.

Clinically significant abnormalities must be reported in the AE CRF.

8.7 Pharmacokinetics

8.7.1 Pharmacokinetics

PK samples will be collected at the timepoints defined in the Assessment Schedule (Section 8.1). Follow instructions outlined in the SOM and Central Laboratory Manual regarding sample collection, numbering, processing and shipment. See Section 8.9 regarding the potential use of residual samples.

In order to better define the PK profile, the timing of the PK sample collection may be altered based on emergent data. The number of samples/blood draws and total blood volume collected will not exceed those stated in the protocol. The changes will be communicated to participating sites in a protocol or SOM amendment.

PK samples will be obtained and evaluated in all patients at all dose levels except the placebo group.

Corporate Confidential Information

Concentrations will be expressed in mass per volume units.

Concentrations below the LLOQ will be reported as “zero” and missing data will be labeled as such in the Bioanalytical Data Report.

For standard PK abbreviations and definitions see the list provided at the beginning of this protocol.

The following PK parameters will be determined using the actual recorded sampling times and non-compartmental method(s) with Phoenix WinNonlin (Version 6.4 or higher): C_{max}, T_{max}, AUC_{last}, AUC_{tau}, T_{1/2}, V_z/F and CL/F from the serum concentration-time data. Some of these PK parameters are exploratory in this study.

The linear trapezoidal rule will be used for AUC calculation. Regression analysis of the terminal serum elimination phase for the determination of T_{1/2} will include at least 3 data points after C_{max}. If the adjusted R² value of the regression analysis of the terminal phase will be less than 0.75, no values will be reported for T_{1/2}, AUC_{inf} and CL/F.

Corporate Confidential Information

Corporate Confidential Information

Corporate Confidential Information

Corporate Confidential Information

9 Safety monitoring

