3.1 Study design

Figure 3-1 Study Design

This is a non-confirmatory, randomized, patient and investigator-blinded, placebo-controlled, parallel-group study in patients with PAD and intermittent claudication. Approximately 40 randomized patients will be treated in a 1:1 ratio to receive LLG783 or placebo as an i.v. infusion of CCI i.v. dosing once every 4 weeks for a total of 4 doses over a period of 12 weeks/3 months. Key study assessments are conducted at week 16 (month 4) of the study (i.e. after 16 weeks of exposure), which is one month after the final dose of study medication.

The dose may be altered based on review of data from the 1st interim analysis (IA).

Corporate Confidential Information

Potential study participants will undergo screening assessments, including 6MWT and ABI, to determine eligibility. Patients who pass the screening evaluations will come to the investigational site on Day 1, at which time inclusion and exclusion criteria will be re-reviewed, and eligible patients will be randomized and dosing will commence.

Assessments of functional capacity (6MWT) will be made at weeks 8 and 16 (days 57 and 113) following the first dose of study medication, with follow-up functional assessments at weeks 24 and 32 (days 169 and 225) following the first dose of study medication (i.e. 2 and 4 months following the last dose of medication, see [Figure 3-1](#)). These follow-up assessments will be performed to help define durability of clinical response as LLG783 exposure declines. The primary endpoint of improved walk distance will be adjudicated based on the 8 and 16 week data points, though the 24 and 32 week data may be used in final statistical modeling.

Safety assessments will include physical examinations, ECGs, vital signs, standard clinical laboratory evaluations (hematology, blood chemistry, and urinalysis), as well as AE and SAE monitoring.

Patients who discontinue the study for reasons other than safety prior to the week 16 visit may be replaced in order to ensure ability to assess 40 patients with a functional assessment after 16 weeks of exposure.

Corporate Confidential Information

Corporate Confidential Information

Corporate Confidential Information

Corporate Confidential Information

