11.5 Analysis of secondary variable(s)

11.5.1 Pharmacokinetics

LLG783 serum concentrations will be listed by treatment, patient, and visit/sampling time point. Descriptive summary statistics will be provided by treatment and visit/sampling time point, including the frequency (n, %) of concentrations below the LLOQ and reported as zero.

Pharmacokinetic parameters will be calculated as described in [Section 8.7.1](#) and will be listed by treatment and patient and summarized by treatment and visit. Summary statistics will include mean (arithmetic and geometric), SD, CV (arithmetic and geometric), median, minimum and maximum. An exception to this is Tmax where median, minimum and maximum will be presented.

Concentrations below LLOQ will be treated as zero in summary statistics and for PK parameter calculations. A geometric mean will not be reported if the dataset includes zero values.

Corporate Confidential Information

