1.3.2 Secondary objective(s)

Secondary objective(s)	Endpoints related to secondary objectives
------------------------	---

• To investigate the PK of LLG783 in subjects with PAD and intermittent claudication.	
• PK parameters will be determined, including: AUCinf, AUClast, AUC0-t, AUC0tau, Cmax and Tmax

• To evaluate the effect of LLG783 on symptomatic functional capacity after 3 months of treatment in subjects with PAD and intermittent claudication.	
• Pain-free walking distance assessed by 6MWT

Corporate Confidential Information

Corporate Confidential Information

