5.1 Variables

Corporate Confidential Information

If data permit and as applicable, the following pharmacokinetic parameters for the parent LLG783 will be determined using the actual recorded sampling times and non-compartmental method(s) with Phoenix WinNonlin (Version 6.4 or higher) from the serum concentration data.

- PK parameters related to secondary objectives:
 - AUC_{inf}, AUC_{last}, AUC_{0-t}, AUC_{0tau}, C_{max}, T_{max}.

Corporate Confidential Information

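### Protocol 8.7.1 withholds T1/2, AUCinf and CL/F after a rejected terminal fit but not Vz/F, and does not visibly say which dose or which AUC gives AUCinf and clearance

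*Protocol*

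**What the plan says.** Protocol 8.7.1 plans a non-compartmental derivation of Cmax, Tmax, AUClast, AUCtau, T1/2, Vz/F and CL/F, and adds that "Some of these PK parameters are exploratory in this study". AUCinf is missing from that list, although Protocol 2.2 and SAP 1.3.2 make it a secondary endpoint: "PK parameters will be determined, including: AUCinf, AUClast, AUC0-t, AUC0tau, Cmax and Tmax". It appears in 8.7.1 only in the suppression rule.

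Two conditions on the terminal phase are visible in 8.7.1. The regression "will include at least 3 data points after" Cmax, and if the adjusted R-squared of the "regression analysis of the terminal phase will be less than 0.75, no values will be reported for" T1/2, AUCinf and CL/F. On integration: "The linear trapezoidal rule will be used for AUC calculation".

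Protocol 11.5.1 says that PK parameters "will be listed by treatment and patient and summarized by treatment and visit". SAP 5.1 repeats the secondary list under the label "PK parameters related to secondary objectives", subject only to a general proviso that the data allow it. Neither document visibly assigns AUCinf or CL/F to a dose, or says which AUC gives clearance.

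Dosing is "once every 4 weeks for a total of 4 doses over a period of 12 weeks/3 months" (Protocol 3.1), that is Days 1, 29, 57 and 85. As I read Table 8-1, whose layout is broken in the copy I had, the later PK samples after dose 1 are on Days 4, 15 and 29, with dose 2 on Day 29. Those after dose 4 are on Days 95, 113, 156, 169 and 225.

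**The concern.** The suppression rule is internally inconsistent. T1/2, AUCinf and Vz/F all depend on the terminal slope, so a slope judged unfit for the first two is unfit for the third. As written, a patient whose fit fails would have no half-life in the listing but would still have a volume calculated from that half-life.

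The rule also raises the question of where CL/F comes from. Clearance from AUCtau needs no terminal slope, so tying CL/F to the fit only makes sense if it is Dose/AUCinf. That is sound after a single dose. After dose 4 the area to infinity also contains drug remaining from doses 1 to 3, and Dose/AUCinf is then too low.

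Finally, R-squared measures how straight the log-linear tail is, not how much of AUCinf lies beyond the last sample. After dose 1 everything past 28 days is extrapolated, because dose 2 intervenes. A reader of the by-visit summary could take a value that is half extrapolated for an observed exposure.

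**Working it through.** The documents state no half-life, extrapolated share or expected clearance, so there is no planned figure to reproduce.

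**1. Dependence on the slope (no assumptions).** With terminal slope λz: T1/2 = ln 2/λz; AUCinf = AUClast + Clast/λz; Vz/F = (CL/F)/λz. CL/F = Dose/AUCinf needs λz, and Dose/AUCtau does not. So Vz/F needs λz whichever AUC gives clearance, and it is the one slope-dependent parameter left off the list.

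**2. Size of the dose-1 and dose-4 effects.** From the documents: interval 28 days, four doses. Assumed: half-life 7 to 28 days, linear one-compartment kinetics, bolus approximation. Let r = 2^(−28/half-life).

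- Extrapolated share of AUCinf after dose 1 = r.
- AUCinf from dose 4 relative to a single dose: R = 1 + r + r² + r³.
- Understatement of clearance by Dose/AUCinf at dose 4 = 1 − 1/R.
- AUCtau at dose 4 relative to single-dose AUCinf = (1 − r)R = 1 − r⁴.

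| Half-life (days) | r | R | Clearance understated by Dose/AUCinf, dose 4 | 1 − r⁴ |
|---|---|---|---|---|
| 7 | 0.0625 | 1.07 | 6% | 1.000 |
| 14 | 0.250 | 1.33 | 25% | 0.996 |
| 21 | 0.397 | 1.62 | 38% | 0.975 |
| 28 | 0.500 | 1.88 | 47% | 0.938 |

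Dose/AUCtau therefore overstates clearance by at most 1/0.9375 − 1 = 6.7% in this range. A two-compartment check (fast-phase half-life 2 days, equal intercepts) gives extrapolated shares of 5, 22, 36 and 47%.

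**3. Integration error.** The table uses exact areas. The linear rule on sparse samples adds an upward error. With dose-4 points at 0, 10 and 28 days and a 7-day half-life, relative concentrations are 1, 0.371 and 0.0625. The trapezoids sum to 10 × 1.371/2 + 18 × 0.434/2 = 10.76, against an exact 0.9375/0.0990 = 9.47, which is 14% too high. The same sum gives 4, 2 and 1% at 14, 21 and 28 days. This error enters AUCinf as well, so it does not favour Dose/AUCinf.

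**4. What the R-squared rule does on the dose-1 schedule.** Simulated three-point fits (Days 4, 15, 29), median half-life 21 days, between-patient CV 40%, residual CV 20%, all assumed. The slowest quarter of patients passes 49% of the time and the fastest quarter 90%. The geometric mean true AUCinf of those passing is 0.92 of the whole group, and 90% of those passing still have more than 20% extrapolated. Over median half-lives of 14 to 28 days and residual CVs of 15 to 30%, the ratio runs from 0.89 to 0.98. The rule does not detect dose-4 carry-over: the dose-4 fit passes in at least 98.6% of simulated profiles in every case tried.

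**5. Would excluding values above 20% extrapolated help?** Same model, median half-lives 14, 21 and 28 days:

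| Rule | Profiles kept | Geometric mean true AUCinf, kept / all |
|---|---|---|
| R-squared only | 85, 70, 58% | 0.95, 0.92, 0.90 |
| R-squared plus 20% exclusion | about 37, 11, 3% | about 0.71, 0.57, 0.49 |

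The exclusion makes the selection of fast eliminators much worse.

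**The case against.** The strongest reply is that much of this cannot be shown from the visible text. Confidential material is removed next to the parameter lists in both Protocol 8.7.1 and SAP 5.1, and an extrapolation limit, a profile day or a clearance formula may sit there. That stands: one can say that no limit is visible, not that none exists.

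The half-life is also unseen. At 7 days every bias in the section 2 table is about 6% or less. Target-mediated disposition is in the abbreviation list, so linearity is not assured either. That stands too, and it is why a range is given.

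The use of Dose/AUCinf at dose 4 is inferred. AUCtau is among the planned parameters, and a summary by visit does not mean that AUCinf is derived at every visit. CL/F, T1/2 and Vz/F are not secondary endpoints, and the PK summaries are descriptive.

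Four stronger readings are tempting, and the documents support none of them:

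- That R-squared is the only acceptance test: 8.7.1 also requires three points after Cmax.
- That both profiles necessarily give biased values: this depends on the half-life, and at dose 4 on an unstated formula.
- That slow eliminators are filtered out: they are reported less often, and the shift in the geometric mean is about 2 to 11% in the cases tried.
- That the dose review at the first interim analysis rests on an extrapolated AUCinf: SAP section 3 speaks of exposure and visibly names no parameter.

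None of this touches Vz/F. The sentence listing the withheld parameters is complete and unredacted.

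**Conclusion.** The omission of Vz/F is a definite inconsistency and needs no assumption. The source of CL/F is a genuine ambiguity. On one reading (Dose/AUCinf after dose 4) clearance is understated by 6 to 47% for half-lives of 7 to 28 days. On the other (Dose/AUCtau) the error before integration is at most 6.7%, and withholding CL/F on the terminal fit discards usable values. AUCinf after dose 1 is 6 to 50% extrapolated over the same range and carries no visible flag. All these sizes rest on assumed half-lives and linear kinetics.

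Severity is minor. Only AUCinf is a named secondary endpoint, no visible decision rule uses it or CL/F, and AUCtau is already planned.

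**What to change.** In Protocol 8.7.1 and SAP 5.1:

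- Add Vz/F to the parameters withheld when the terminal fit fails.
- Define dose-4 clearance as Dose/AUCtau over Days 85 to 113, and do not withhold it on the terminal fit.
- Report AUCinf for dose 1 only. List and flag percent extrapolated, and give the number of profiles withheld. Do not exclude values above 20%, for the reason shown in the working.
- Use AUCtau as the exposure measure by visit.
- Estimate T1/2 from the samples after dose 4 out to Day 225, using those that are quantifiable. Under linear kinetics carry-over does not bias that slope.

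If redacted text already settles any of these, it only needs to agree with the visible rule.

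The cost is minor wording and programming, with no new samples. The downside is that flagged AUCinf values stay in the summaries and need cautious reading.

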9.1 Adverse events

An AE is any untoward medical occurrence (i.e., any unfavorable and unintended sign, including abnormal laboratory findings, symptom or disease) in a patient after *providing written informed consent* for participation in the study until the end of study visit. Therefore, an AE may or may not be temporally or causally associated with the use of a medicinal (investigational) product.

In addition, all reports of intentional misuse and abuse of the study treatment are also considered an AE irrespective if a clinical event has occurred. See [Section 9.5](#) for an overview of the reporting requirements.

The occurrence of AEs must be sought by non-directive questioning of the patient at each visit during the study. Adverse events also may be detected when they are volunteered by the patient during or between visits or through physical examination finding, laboratory test finding, or other assessments.

Abnormal laboratory values or test results constitute AEs only if they fulfill at least one of the following criteria:

- they induce clinical signs or symptoms,
- they are considered clinically significant,
- they require therapy.

Clinically significant abnormal laboratory values or test results should be identified through a review of values outside of normal ranges/clinically notable ranges, significant changes from screening or the previous visit, or values which are considered to be non-typical in patients with underlying disease. Investigators have the responsibility for managing the safety of individual patient and identifying adverse events. Alert ranges for liver and kidney related events are included in [Appendix 1](#) and [Appendix 2](#), respectively.

Adverse events should be recorded on the Adverse Events CRF under the signs, symptoms or diagnosis associated with them, and accompanied by the following information:

1. The severity grade
 - mild: usually transient in nature and generally not interfering with normal activities
 - moderate: sufficiently discomforting to interfere with normal activities
 - severe: prevents normal activities
2. its relationship to the study treatment
 - Yes or
 - No
3. its duration (start and end dates) or if the event is ongoing an outcome of not recovered/not resolved must be reported.
4. whether it constitutes a SAE (see [Section 9.2](#) for definition of SAE) and which seriousness criteria have been met
5. Action taken regarding investigational treatment.
All AEs must be treated appropriately. Treatment may include one or more of the following:
 - no action taken (e.g. further observation only)
 - investigational treatment interrupted/withdrawn
 - concomitant medication or non-drug therapy given
 - hospitalization/prolonged hospitalization (see [Section 9.2](#) for definition of SAE)
6. its outcome (not recovered/not resolved; recovered/resolved; recovering/resolving, recovered/resolved with sequelae; fatal; or unknown).

Information about common side effects already known about the investigational drug can be found in the IB or will be communicated between IB updates in the form of Investigator Notifications. Once an AE is detected, it must be followed until its resolution or until it is judged to be permanent, and assessment should be made at each visit (or more frequently, if necessary) of any changes in severity, the suspected relationship to the investigational drug, the interventions required to treat it, and the outcome.

The investigator must also instruct each patient to report any new adverse event (beyond the protocol observation period) that the patient, or the patient's personal physician, believes might reasonably be related to study treatment. This information must be recorded in the investigator's source documents; however, if the AE meets the criteria of an SAE, it must be reported to Novartis.

*Refer to the SOM for data capture methodology regarding AE collection for patients that fail screening.

9.2 Serious adverse event reporting

9.2.1 Definition of SAE

An SAE is defined as any AE [appearance of (or worsening of any pre-existing) undesirable sign(s), symptom(s) or medical conditions(s)] which meets any one of the following criteria:

- is fatal or life-threatening
- results in persistent or significant disability/incapacity
- constitutes a congenital anomaly/birth defect in offspring
- requires inpatient hospitalization or prolongation of existing hospitalization, UNLESS the hospitalization is for:
 - routine treatment or monitoring of the studied indication, not associated with any deterioration in condition (e.g. critical limb ischemia)
 - elective or pre-planned treatment for a pre-existing condition (that is unrelated to the indication under study and has not worsened since the start of study drug;
 - treatment on an emergency outpatient basis for an event not fulfilling any of the definitions of a SAE given above and not resulting in hospital admission;
 - social reasons and respite care in the absence of any deterioration in the patient's general condition.
- is medically significant, e.g. defined as an event that jeopardizes the patient or may require medical or surgical intervention.

NOTE that all malignant neoplasms will be assessed as serious under "medically significant" if other seriousness criteria are not met.

Life-threatening in the context of a SAE refers to a reaction in which the patient was at risk of death at the time of the reaction; it does not refer to a reaction that hypothetically might have caused death if it were more severe (please refer to [ICH-E2D Guideline 2004](#)).

Medical and scientific judgment should be exercised in deciding whether other situations should be considered serious reactions, such as important medical events that might not be immediately life threatening or result in death or hospitalization but might jeopardize the patient or might require intervention to prevent one of the other outcomes listed above. Examples of such events are intensive treatment in an emergency room or at home for allergic bronchospasm, blood dyscrasias or convulsions that do not result in hospitalization or development of dependency or abuse (please refer to [ICH-E2D Guideline 2004](#)).

Any suspected transmission via a medicinal product of an infectious agent is also considered a serious adverse reaction.

All AEs (serious and non-serious) are captured on the CRF; SAEs also require individual reporting to Novartis Chief Medical Office and Patient Safety (CMO & PS) as per [Section 9.2.2](#).

